6. STATISTICAL METHODS

General considerations

Continuous variables will be reported with parametric (mean/standard deviation) or non-parametric (median, quartiles) descriptive statistics, depending on the distribution. Ordinal/nominal variables will be reported as frequency tabulation. All statistical tests will be carried out two-sided. A p-value ≤ 0.05 is considered statistically significant throughout.

Predictor analysis

In part 1, the relationship between each potential predictor variable and the primary outcome variable will first be explored in univariate logistic regression analyses. Collinearity between predictor variables will be assessed by correlation analyses, and dimensionality reduction by PCA will eventually be considered. Then, all variables with a p-value ≤ 0.25 in the univariable analyses will be included in the first modelling step. In order to obtain a more parsimonious model, the combination of variables that gives the lowest Akaike Information Criteria (AIC) will constitute the final model. The value of predictor(s) in the final multivariable model will be assessed through the construction of Receiver Operating Characteristics (ROC) curves, and calculation of negative predictive value.

In part 2, the prediction model from part one will be validated by including a total of n~125 individuals with known CHD in the study population. The prediction model should correctly classify all these cases; if not, the model will be adjusted. We aim for zero false negatives, i.e. all cases with cardiac abnormalities in need of intervention and/or hospital follow-up should be identified. To explore the potential of the prediction model to classify all cases based upon this premise, we will apply different combinations of levels of the identified predictor variables.

Cross-sectional analyses

For the secondary study aims, cross-sectional analyses across cases and controls are feasible. Such analyses will feature parametric tests (Student t), non-parametric tests (Mann-Whitney), regression analyses or table analyses (Chi-square, Fisher) as appropriate.

Sensitivity analyses

Throughout, sensitivity analyses applying a different classification of caseness in the primary outcome variable will be carried out:

1. Caseness defined as all abnormalities identified by echocardiography, independent of intervention/follow-up needs
2. Caseness defined as all abnormalities in need of surgical or catheter-based intervention

Cardiac murmurs in children: Predictive value of cardiac markers (CAMUS)

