3. OTHER VARIABLES

The main analysis is aimed to construct a prediction model for CHD that can be applied in general practice. The analysis will entail bivariate logistic regression between potential predictor (independent) variables and the primary outcome variable (cf. above), followed by multivariable logistic regression modelling and construction of receiver operating curves (ROC).

Relevant predictor (independent) variables include (but are not restricted to):

- *Background*: Sex, age, ethnicity, weight/height
- *Clinical symptoms*: Breathlessness, exertion intolerance/low physical fitness, sweating, reduced general condition
- *Routine clinical findings*: Heart rate, respiratory rate, SaO₂, murmur characteristics, blood haemoglobin,
- *ECG characteristics*: PR interval, QRS interval, QRS axis, Sokolow-index
- *Blood biomarkers*: NT-proBNP, troponin T, hsCRP, IL-6

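### The blanket 0.05 rule labels terms of a model selected on the same children as statistically significant, although their p-values are no longer valid as ordinary tests

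*SAP*

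**What the plan says.** Section 6, General considerations, sets one rule for every test: "All statistical tests will be carried out two-sided", and "A p-value ≤ 0.05 is considered statistically significant throughout". It gives no hierarchy, no adjustment and no exemption.

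The Predictor analysis part of section 6 then describes three steps:

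- First, "the relationship between each potential predictor variable and the primary outcome variable will first be explored in univariate logistic regression analyses".
- Next, "all variables with a p-value ≤ 0.25 in the univariable analyses will be included in the first modelling step".
- Finally, the combination with the lowest AIC becomes the final model, which is assessed by ROC curves and negative predictive value.

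Section 3 supplies the candidates and leaves the list open: "Relevant predictor (independent) variables include (but are not restricted to". It names background items ("Sex, age, ethnicity, weight/height"), symptoms ("Breathlessness, exertion intolerance/low physical fitness, sweating, reduced general condition"), routine findings ("Heart rate, respiratory rate, SaO₂, murmur characteristics, blood haemoglobin"), four ECG measures and four blood biomarkers.

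Section 4 uses a different level, α = 0.01, for the sample size. Section 6 does not refer to it.

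**The concern.** The wording of the univariable step suggests exploration. The final-model terms carry no such label, so the blanket rule applies to them. Those terms survive two data-driven filters on the same children, and both filters favour small p-values. An ordinary Wald or likelihood-ratio p-value computed afterwards ignores that selection.

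Section 3 says the model is meant for use in general practice. Followed as written, the SAP lets a symptom, ECG measure or inflammatory marker be reported as a statistically significant predictor of heart disease when it is noise. This point concerns claims about single predictors. It does not concern optimism in the AUC or the model's discrimination.

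**Working it through.** **Number of tests.** Section 3 lists 4 background + 4 symptom + 5 routine clinical + 4 ECG + 4 biomarker items = 21. Weight/height and murmur characteristics are each counted once, and the list is open, so 21 is a minimum.

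**Number of cases.** Section 4 gives 2% prevalence, so 0.02 × 400 = 8 cases and 0.02 × 500 = 10 cases.

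**The plan's own figure.** The SAP states no family-wise rate, so there is none to reproduce. Its sample size can be reproduced, which shows what test it seems to have in mind.

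- Assume AUC 0.85 against 0.5 (the null value is not stated), two-sided α = 0.01 and Hanley–McNeil standard errors.
- With 8 cases and 392 controls, the standard error is 0.1032 under the null and 0.0859 under the alternative.
- Power = Φ[(0.35 − 2.576 × 0.1032)/0.0859] = Φ(0.98) = 0.84.
- The exact requirement for 80% power is 374 children (7.48 cases). Rounding up to 8 cases gives 8/0.02 = 400, and 400/0.8 = 500 with drop-out.

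**Univariable step alone.** For 21 independent tests at 0.05, P(at least one false positive) = 1 − 0.95^21 = 0.66. At the 0.01 of section 4 it would be 1 − 0.99^21 = 0.19.

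**A term kept by AIC.** AIC keeps a one-parameter term when its likelihood-ratio chi-square exceeds 2, which corresponds to p < 0.157. For an independent null term, P(p ≤ 0.05 given retained) ≈ 0.05/0.157 = 0.32. This argument is made term by term. It does not need every other predictor to be useless.

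**Simulation of the written sequence.** There are 21 normal predictors and no true effects. The steps are univariable Wald p ≤ 0.25, backward search to lowest AIC, then Wald p ≤ 0.05 in the final model. The results below are for 500 children and 10 cases, with the same assumed correlation between all predictors. Ranges span repeated runs, some of which used yes/no predictors at correlation 0.8. With 400 runs the Monte Carlo standard error is about 0.025.

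| Assumed correlation | Any univariable p ≤ 0.05 | Any final-model term p ≤ 0.05 | Share of retained null terms with p ≤ 0.05 |
|---|---|---|---|
| 0 | 0.63–0.64 | 0.66–0.69 | 0.33–0.34 |
| 0.5 | 0.43 | 0.55–0.59 | 0.57–0.58 |
| 0.8 | 0.23–0.24 | 0.18–0.31 | 0.34 |

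With 400 children and 8 cases, the final-model figures are 0.67 (correlation 0) and 0.56 (0.5).

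**Other correlation patterns.**

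- Correlation only within each predictor group, from 0 to 0.7: 0.69 down to 0.51 for any final-model term.
- Age-driven correlation with yes/no symptoms present in 2–10% of children: 0.40–0.54 for the univariable step and 0.47–0.61 for final-model terms.

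**The case against.** The strongest reply is that 0.05 decides nothing here. Entry is at p ≤ 0.25, AIC picks the model, and ROC curves and negative predictive value judge it. Part 2 then tests it on known cases. No sentence says that a predictor will be adopted or dropped because p ≤ 0.05. This stands, and it limits the harm to what is reported. It does not make the label valid, because the blanket rule still applies it to the selected terms.

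Two stronger readings are tempting, and the document supports neither.

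- A reader might infer that a spurious significant predictor is more likely than not. That holds for independent or moderately correlated predictors. It fails at a correlation of 0.8 and is borderline in the age-driven settings. The SAP gives no correlations. The case where no predictor works is also only a benchmark, because section 4 itself assumes an AUC of 0.85 for NT-proBNP.
- A reader might divide 0.55–0.69 by 0.05 and speak of an 11- to 14-fold inflation. That compares a family-wise rate with a per-test threshold. The SAP never claims family-wise control at 0.05.

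The simulations also leave out the collinearity check and the possible PCA, and most treat all predictors as continuous. The exact percentages are therefore indicative.

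**Conclusion.** The point holds as one about validity and reporting. The SAP's rule attaches a significance label to terms for which an ordinary p-value is no longer a test. With no true effects, roughly one third to nearly 60% of retained terms would earn the label instead of 5%. The chance of at least one such term ranges from about 0.68 (independent predictors) through 0.55 (correlation 0.5) to 0.2–0.3 (correlation 0.8). These figures rest on 8 to 10 cases, 21 candidates and assumed correlations.

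The choice of model and its assessment by ROC curves and negative predictive value do not depend on the 0.05 label. The point should be corrected, but it does not undermine the main analysis.

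**What to change.** Limit the blanket sentence in section 6 by adding:

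*P-values in the univariable step serve screening only. Terms of the AIC-selected model are reported as estimates with their bootstrap selection frequency, with the screen and the AIC step repeated in each resample. No term is called statistically significant.*

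Section 6 names no primary test. If a confirmatory claim is wanted, the sponsor should name the test, for example the NT-proBNP AUC against 0.5 that the sample size appears to assume. Its level should then be reconciled with the α of 0.01 in section 4. If no such claim is wanted, the SAP should state that all p-values are exploratory.

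The cost is a change of wording and a short bootstrap that needs no extra data. Individual predictors can no longer be reported as significant. With 8 to 10 expected cases the selection frequencies will themselves be unstable, and the report should say so.

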2. ENDPOINT

Outcome variable

The primary outcome variable in part 1 is a diagnosis of cardiac disease based upon echocardiographic assessment. The diagnostic process will adhere to international consensus guidelines on paediatric cardiology (Doshi & Chikkabryappa, 2018; Sachdeva et al., 2020; Writing Committee et al., 2021). Thereafter, all participants will be assigned to either of two groups: a) A cardiac diagnosis that needs intervention/treatment and/or further clinical follow-up (cases); b) No cardiac diagnosis or a cardiac

Cardiac murmurs in children: Predictive value of cardiac markers (CAMUS)

diagnosis that does not need intervention/treatment and/or further clinical follow-up (controls). Hence, the primary outcome variable is dichotomous. The assignment to cases vs. controls will follow pre-defined criteria pertaining to each cardiac diagnosis/diagnostic group (Table 2).

In part 2, all participants are assigned as cases, as per the inclusion criterium of a confirmed cardiac anomaly in need of intervention.

Table 2. Criteria for assignment of cases (need of intervention and/or clinical follow-up) vs. controls (no need of intervention nor clinical follow-up)	
Primary cardiac diagnosis	Criteria for caseness (only one criterium needs to be fulfilled per diagnosis)
Persistent foramen ovale (PFO)	N/A (never assigned as case)
Atrial septal defect (ASD), all subgroups	Case if: 
 - Ostium premium defect - Sinus venosus defect - Ostium secundum defect diameter > 3 mm OR with signs of right atrium volume load.
Persistent ductus arteriosus (PDA)	Case if: 
 - Ductus diameter >1.5 mm. - LA/Ao ratio >1.5 - Retrograde diastolic flow in the abdominal aorta. - Continuous murmur
Ventricular septum defect (VSD), all subgroups	Case if 
 - Perimembranous location - Inlet location - Subpulmonary outlet/supracristal location - Muscular location with diameter >5 mm OR left ventricular dilatation OR Qp/Qs ≥1.5. - Multiple defects
Aortic valve pathology (stenosis (AS), regurgitation (AR), bicuspid valve)	Case if: 
 - Flow velocity ≥ 2.0 m/s. - Hypertrophy of left ventricle. - Aortic regurgitation (more than trivial)

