4. SAMPLE SIZE CONSIDERATIONS

The value of possible predictors will be assessed through the construction of Receiver Operating Characteristics (ROC) curves, and calculation of negative predictive value. Based upon register data from the outpatient clinical at Ahus, the prevalence of cardiac disorder in the population under study is estimated at 2 %. The area under the ROC-curve for NT-proBNP in a previous study with similar methodology has been established at 0.85 (Law et al, 2009). The possible clinical application of the results from the present study requires a very low risk of false negatives (ie. no patients with cardiac disorders should be deemed healthy based upon a certain cardiac marker). Therefore, the level of significance (α) is set to 0.01. Given a test power ($1 - \beta$) = 0.8, sample size is estimated at 400 patients. A drop-out rate of up to 20 % might be assumed (technical problems, refusal of blood sampling, etc), therefore a total of 500 patients should be included in the study.

In part 2, when a population of 125 patients with well-defined CHD is added to the population of about 500 individuals previously recruited, the ratio of cases:controls increases to about 0.25. This will enable an α -value less than 1×10^{-10} , and a power ($1 - \beta$) of comparable magnitude, which we find satisfactory.

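### Part 1 picks its model from at least 21 candidates with 8–10 expected cases and reports ROC and NPV on the same children, with no correction for optimism

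*SAP*

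**What the plan says.** Section 3 calls the prediction model the main analysis and gives its candidates under an open heading: "Relevant predictor (independent) variables include (but are not restricted to". Section 4 states that "the prevalence of cardiac disorder in the population under study is estimated at 2" per cent, and arrives at 400 evaluable and 500 recruited children.

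Section 6 sets the selection in two steps. First, "all variables with a p-value ≤ 0.25 in the univariable analyses will be included in the first modelling step". Second, "the combination of variables that gives the lowest Akaike Information Criteria (AIC) will constitute the final model". Evaluation follows directly: "The value of predictor(s) in the final multivariable model will be assessed through the construction of Receiver Operating Characteristics (ROC) curves", together with NPV. Correlation analyses are planned and PCA is left as something to consider. No bootstrap, cross-validation, split sample, shrinkage or penalisation is named.

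For part 2, Section 6 says the model "will be validated by including a total of n~125 individuals with known CHD in the study population", and adds: "The prediction model should correctly classify all these cases; if not, the model will be adjusted". Section 2 fixes who these children are: "In part 2, all participants are assigned as cases, as per the inclusion criterium of a confirmed cardiac anomaly in need of intervention".

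**The concern.** A model chosen by a liberal p-value screen and then by AIC has been fitted to the accidents of its own sample. Measured on that sample, its AUC is too high, and the excess grows as cases per candidate fall. Here there are fewer cases than candidates.

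The part 1 AUC of the selected model would be a headline result on predictive value, and readers could not tell how much of it is real. NPV does not expose the problem, because at 2% prevalence calling every child healthy already gives an NPV of 98%. The plan aims for no missed cases with a tool for general practice, so a cut-off that looks perfect only on its own data is the error that matters most.

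**Working it through.** **1. The plan's sample size.** Inputs from Section 4: AUC 0.85, α = 0.01, power 0.80, prevalence 2%. Section 6 makes tests two-sided. A null AUC of 0.5 is assumed, as none is stated. Hanley–McNeil variance with n1 cases and n0 = 49·n1 controls:

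V(A) = [A(1−A) + (n1−1)(A/(2−A) − A²) + (n0−1)(2A²/(1+A) − A²)] / (n1·n0)

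Power = Φ[(0.35 − 2.576·√V(0.5)) / √V(0.85)]

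- n1 = 8, n0 = 392: (0.35 − 2.576 × 0.1032)/0.0859 = 0.98, power 0.84.
- n1 = 7, n0 = 343: (0.35 − 2.576 × 0.1104)/0.0919 = 0.71, power 0.76.

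So 8 cases are needed, 8/0.02 = 400, and 400/(1 − 0.2) = 500. The plan's figures are reproduced, but they are for the AUC of one marker, not for multivariable selection.

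**2. Cases per candidate.** Section 3 lists 4 background + 4 symptoms + 5 clinical findings + 4 ECG + 4 biomarkers = 21, counting weight/height, ethnicity and murmur characteristics once each. Expected cases are 0.02 × 400 = 8 or 0.02 × 500 = 10 (central 95% binomial ranges 3–14 and 4–17). Cases per candidate: 8/21 = 0.38 or 10/21 = 0.48. If none of the 21 predicted anything, 0.25 × 21 = 5.25 would still be expected to pass the screen.

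**3. Size of the optimism.** Simulation of the stated procedure: Wald p ≤ 0.25 screen, then backward elimination to lowest AIC, 300 datasets per setting, true AUC measured in test sets of 4,000. There is one true marker with AUC 0.85 and 20 independent noise variables. Each cell gives apparent vs true mean AUC, first with 14 continuous and 7 binary candidates, then with all continuous.

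| Prevalence | n = 400 | n = 500 | Excess |
|---|---|---|---|
| 2% (plan) | 0.906 vs 0.792; 0.920 vs 0.777 | 0.901 vs 0.796; 0.905 vs 0.789 | 0.10–0.14 |
| 5% (assumed) | 0.881 vs 0.818; 0.882 vs 0.818 | 0.873 vs 0.824; 0.876 vs 0.822 | 0.05–0.06 |
| 10% (assumed) | 0.867 vs 0.830; 0.869 vs 0.830 | 0.864 vs 0.835; 0.868 vs 0.834 | 0.03–0.04 |

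Repeat runs with separate code gave excesses of 0.11–0.16, 0.06–0.07 and 0.03–0.04. With 11 of the 21 candidates correlated at 0.5–0.8, the excess is 0.03–0.13 at 2%, 0.02–0.07 at 5% and 0.01–0.04 at 10%. With no true predictor (true AUC 0.50), the apparent AUC at 2% is 0.69–0.79, and up to 0.83 in repeat runs. A single pre-specified marker without selection shows an excess of about 0.00.

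**4. A cut-off with no misses.** If the cut-off is set so that no part 1 case is missed, apparent sensitivity and NPV are both 100%. In the one-marker setting at 2%, mean true sensitivity is 0.66 (8 cases) or 0.76 (10 cases), and true NPV is about 0.99, against 0.98 for a useless test.

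**5. Part 2.** With 125 cases added to part 1 at 2% prevalence (200 datasets), the unadjusted model's pooled AUC compares with its true AUC in children with murmurs as follows:

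- Part 2 cases like part 1 cases: 0.80–0.81 vs 0.79–0.80.
- Marker levels 1.25–1.5 times as far from controls (assumed): 0.85–0.90 vs 0.78–0.80, an excess of 0.06–0.10. A model refitted on the pooled data is then 0.06–0.09 too high.

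**6. What a bootstrap recovers.** Repeating the whole search in 100 resamples (200 datasets, 2%), apparent / corrected / true AUC is 0.901 / 0.815 / 0.797 for n = 500 and 0.909 / 0.817 / 0.793 for n = 400.

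**The case against.** Five points can be made for the plan.

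- **PCA.** It is the plan's one response to many candidates. Replacing the 11 correlated variables by their first component gives an excess of 0.07–0.09 at 2%, against 0.08–0.13 without it. But PCA is optional in the text, and most of the bias remains.
- **Prevalence.** The 2% comes from register data on cardiac disorder, whereas Table 2 also counts findings that need only follow-up. True caseness may be higher and the excess smaller. This stands, and is why 5% and 10% are shown. The excess stays positive in every setting examined.
- **Part 2 is new data.** Before any adjustment, the added children do give an independent check of sensitivity, and the pooled AUC would be nearly right if they resembled part 1 cases. The shift of 1.25–1.5 is an assumption. The documents support only its direction: part 2 cases all need intervention, and the exclusions for other disorders and medications apply to part 1 only. What holds without the assumption is that no new controls are added, so specificity and NPV are never tested on new children. Once the model is adjusted to these cases, the sensitivity check is no longer independent.
- **Single markers.** The primary aim concerns cardiac markers, and one pre-specified marker suffers no such bias. This limits the finding to the selected multivariable model, which Section 3 makes the main analysis.
- **The remedy is imperfect** with so few cases. This also stands; its limits are given with the fix.

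**Conclusion.** The concern holds and must be fixed. Followed as written, the plan reports a part 1 AUC for the selected model that is biased upwards: by about 0.10–0.14 at its own 2% prevalence with independent candidates, or 0.03–0.13 with about half of them correlated. At an assumed 5% or 10% the excess is 0.02–0.07 or 0.01–0.04 across all settings.

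These sizes rest on one true marker at the plan's AUC of 0.85, simulated predictors and backward AIC selection. They show scale and are not forecasts. The direction and the lack of any correction do not depend on them. Part 2 tests sensitivity in a different group of cases and does not correct the part 1 AUC.

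**What to change.** Necessary changes to Sections 3 and 6:

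- Close the candidate list before outcome data are examined.
- Repeat the entire model-building process, including the screen and the AIC step, in at least 500 bootstrap samples. Report optimism-corrected AUC beside the apparent value, and likewise sensitivity, specificity and NPV at any cut-off used.
- Report the unadjusted part 1 model's sensitivity in the part 2 cases before any adjustment. Apply the same bootstrap to any adjusted model.
- Keep the AUC for children with murmurs separate from any AUC that includes part 2 cases.

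Preferred but not essential: replace the p-value screen with a short pre-specified model containing NT-proBNP and troponin, ideally with age and penalised fitting, and label any wider AIC search exploratory. In simulation, a three-variable Firth model of this kind (2%, n = 500, only NT-proBNP truly predictive) gave apparent / corrected / true AUC of 0.859 / 0.832 / 0.837.

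The cost is SAP wording, computing time and a lower reported AUC; no more children are needed. The SAP should state the limits that remain with 8–10 cases. If the wide search is kept, the corrected AUC is still 0.02–0.03 too high. In any one study it departs from the truth with an SD of 0.07–0.09. With no true predictor, the corrected AUC is still about 0.60 for the wide search (apparent 0.76) and 0.54 for the three-variable model (apparent 0.64).

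### The p ≤ 0.25 screen names no test and no rule for empty cells; with about 8 to 10 part 1 cases, the usual Wald p-value would discard a yes/no sign present in every case

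*SAP*

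**What the plan says.** SAP section 6 (Predictor analysis) first relates each candidate predictor to case status by univariate logistic regression. Then "all variables with a p-value ≤ 0.25 in the univariable analyses will be included in the first modelling step", and the combination of variables with the lowest AIC becomes the final model. The same section sets the target: "We aim for zero false negatives".

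The section does not say whether the screening p-value is Wald, score or likelihood-ratio. It names no penalised or exact logistic method and has no rule for a predictor with an empty cell. Fisher's test appears only under the cross-sectional analyses for the secondary aims. The sentence on collinearity and PCA concerns a different problem.

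Section 4 fixes the expected number of cases: "the prevalence of cardiac disorder in the population under study is estimated at 2" per cent, with 400 evaluable and 500 enrolled children. Section 3 lists as candidates "Breathlessness, exertion intolerance/low physical fitness, sweating, reduced general condition", together with murmur characteristics and ethnicity, next to continuous measures such as heart rate, SaO₂, ECG intervals and biomarkers. The coding of the symptoms and murmur features is not given.

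**The concern.** With 8 to 10 cases, a sensitive yes/no sign can easily be positive in all of them. One cell of its 2×2 table is then zero, the maximum-likelihood odds ratio is infinite, and the estimated standard error grows faster than the coefficient. The Wald statistic collapses towards zero and its p-value towards 1, however strong the association.

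A screen based on that p-value rejects a sign that misses no observed case and accepts the same sign once it misses one. For a rule-out model aiming at no missed cases, this ordering is the wrong way round. It also conflicts with the plan's next step, because AIC would favour the discarded variable.

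If a likelihood-ratio p-value is used instead, the variable enters. An ordinary multivariable fit then still has an infinite coefficient and gives every child without the sign a predicted risk of exactly 0, on the evidence of 8 to 10 cases.

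**Working it through.** **Inputs.** From SAP section 4: prevalence 2 %, AUC 0.85, α = 0.01, power 0.8, 400 evaluable, drop-out 20 %, 500 enrolled. From section 6: two-sided tests, entry at p ≤ 0.25. Assumed here: null AUC 0.5, yes/no coding, a sign frequency of about 30 % in controls, and the true sensitivities below.

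**The plan's own figure.** With a 1:49 case-to-control ratio, the requirement is z(0.995) × SE(AUC = 0.5) + z(0.80) × SE(AUC = 0.85) ≤ 0.35, using Hanley-McNeil standard errors.
- 8 cases and 392 controls: 2.576 × 0.1032 + 0.842 × 0.0859 = 0.338, which is sufficient.
- 7 cases and 343 controls: 0.362, which is not.

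So 8 cases are needed, that is 8 / 0.02 = 400 children, and 400 / (1 − 0.20) = 500. Both figures reproduce. Expected cases are 0.02 × 400 = 8 evaluable and 0.02 × 500 = 10 enrolled.

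**Sign in 7/8 cases and 118/392 controls.** Odds ratio = (7 × 274) / (1 × 118) = 16.25, so the log odds ratio is 2.788. SE = √(1/7 + 1/1 + 1/118 + 1/274) = 1.075. z = 2.59 and Wald p = 0.009: **kept**.

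**Same sign in 8/8 cases.** The term 1/1 becomes 1/0, so the estimate and its SE have no finite value. Software reports a Wald p of 0.99 or higher (0.991 or 0.999 depending on the program): **dropped**. The likelihood-ratio statistic stays finite:
- Null log-likelihood: 8 ln(8/400) + 392 ln(392/400) = −39.216.
- Model log-likelihood: 8 ln(8/126) + 118 ln(118/126) = −29.795. The 274 children without the sign contribute 0.
- 2 × (39.216 − 29.795) = 18.84 on 1 df, p = 1.4e-5.
- AIC falls from 80.4 to 63.6.

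**With 10 cases.** 10/10 against 147/490 gives Wald p = 0.998 in one program and 0.990 in another, and likelihood-ratio p = 1.2e-6. 9/10 gives Wald p = 0.004. The pattern is the same.

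**How far the likelihood-ratio test helps.** A sign present in all cases passes p ≤ 0.25 unless it is also in more than about 92 % (8 cases) or 93 % (10 cases) of controls.

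**How often a sign is positive in every case** (true sensitivity to the power of the number of cases):

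| Assumed sensitivity | 8 cases | 10 cases |
|---|---|---|
| 70 % | 6 % | 3 % |
| 80 % | 17 % | 11 % |
| 90 % | 43 % | 35 % |
| 95 % | 66 % | 60 % |

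If caseness were 5 % (assumed; 20 to 25 cases), the 90 % row would fall to 12 % and 7 %.

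**The other empty cell.** A sign in 4/8 cases and 0/392 controls has Wald p = 0.999 and likelihood-ratio p = 6e-9. It is also dropped under Wald, but it misses half the cases.

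**Continuous markers.** One simulated marker with AUC 0.85 per sample size gave Wald p of about 1e-4 or less, so it passes.

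**The case against.** **The SAP never names the Wald test.** This stands. A reader might infer that the plan as written necessarily drops every such sign. It does not: under a likelihood-ratio p-value nearly all of them pass. The defect is that the outcome is left to a software default, and the usual default is the harmful one.

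**Not every empty cell concerns a zero-miss predictor.** This stands too. A sign found in no control is perfectly specific in the sample, but its sensitivity may be as low as 1/8. Its loss is a loss of specificity, not of rule-out ability.

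**The scope is limited.** Section 1 names NT-proBNP and hs-troponins as the most relevant markers. Continuous measures are affected only if cases and controls do not overlap at all. Symptoms and murmur features are affected only if coded as categories, and nothing in the SAP shows that any of them reaches 85 to 95 % sensitivity. At 50 % the chance of 8/8 is 0.4 %.

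**An observed 8/8 does not prove a best predictor.** The exact 95 % lower bound on sensitivity is 0.025^(1/8) = 63 % (10/10: 69 %). Part 2 also adds about 125 known cases and allows the model to be adjusted. That step is loosely defined, however, and the SAP gives no rule for bringing back a predictor that the part 1 screen removed.

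**Few events are the root problem.** True, and a change of test does not cure it. It does remove a reversal that serves no purpose.

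**Conclusion.** The point holds in a conditional form. The SAP fixes neither the test behind p ≤ 0.25 nor a method for empty cells. With the 8 to 10 cases its own figures imply, the usual Wald p-value would discard a yes/no sign present in every case and keep the same sign when it misses one. For a sign of 80 to 95 % true sensitivity, this arises in 17 to 66 % of trials with 8 cases and 11 to 60 % with 10. At 70 % it is 6 % and 3 %. These figures assume yes/no coding, the Wald p-value and the 2 % prevalence. They fall if cases are commoner and rise under the planned sensitivity analysis that limits caseness to surgical or catheter-based intervention, if that leaves fewer cases.

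The documents do not support the stronger statements that the screen removes any sign with an empty cell, or that it threatens the main biomarkers. Severity: should-fix.

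**What to change.** Amend SAP section 6 before the data are analysed, since choosing a test after seeing an empty cell would be data-driven:

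- Take the p ≤ 0.25 screening p-value from the likelihood-ratio test, never from the Wald test. It may be the ordinary test, or the Firth-penalised one with the tested coefficient constrained to zero.
- Keep AIC selection on the ordinary likelihood. AIC from the Firth-penalised likelihood depends on measurement units. In one simulated check, a pure-noise covariate had AIC 82.2, 77.6 and 73.0 when rescaled by 0.1, 1 and 10, against 78.3 for the null model, so units alone decided whether it entered.
- Fit the final multivariable model by Firth's method with profile-likelihood intervals, so that an empty cell gives neither infinite coefficients nor predicted risks of exactly 0.
- Apply an intercept correction only if absolute predicted risks are reported. ROC curves, and negative predictive value at a rank-based cut-off, do not need it.

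The cost is SAP wording and a slight shrinkage of coefficients. No extra data are needed.
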